8.5.2 Analysis of secondary endpoints

- (1) Hb values at each evaluation time point in the treatment period
- 1) Hb values at each evaluation time point in the treatment period

Hb value and change of Hb from the first day of the treatment period at each evaluation time point of the treatment period will be obtained, and its descriptive statistics should be calculated for each treatment group. Before and after comparison will be conducted for changes of Hb from the first day of the treatment period to each evaluation time using the paired t-test.

Group comparison will be conducted using an MMRM model (with compound symmetry [CS] for a covariance matrix within subject variance) similar to the analysis of primary endpoint. LSMean, its standard errors, and 2-sided 95% CI will be calculated for Hb value at each evaluation time point of the treatment period, and the point estimate, its standard errors, 2-sided 95% CI, and p-value will be calculated for the group difference (MT-6548 – darbepoetin) of the LSMean by treatment group.

A group comparison will be conducted for the change from the first day of the treatment period using the MMRM model (with compound symmetry [CS] for a covariance matrix within subject variance). LSMean of the change from the first day of the treatment period will be calculated at each evaluation time point of the treatment period, and point estimate, its standard errors, 2-sided 95% CI, and p-value will be calculated for the between-group difference of the LSMean by treatment group.

The time course diagram will be prepared for mean Hb values in each evaluation time point in the treatment period by treatment group. 95% CI of the mean will be represented by an error bar.

The Conversion (Hb value <11.0 g/dL) cohort should be analyzed only in the MT-6548 cohort. No statistical test will be conducted for group differences and the difference between baseline and each evaluation time point in the treatment period for the darbepoetin alfa group in the Conversion cohort and Conversion (Hb value \geq 11.0 g/dL) cohort.

- 2) Analysis of timing of administration of MT-6548 tablets (before meal, after meal, other)

An analysis similar to “1) Treatment period Hb at each evaluation time point in the treatment period” should be conducted by the timing of administration of MT-6548 tablets (before meal, after meal, other). However, this

analysis is only for the MT-6548 group; neither tabulation in the darbepoetin group nor comparison with the darbepoetin group is performed. No analysis will be performed for patient cohorts.

3) Analysis by previous ESA formulation type

An analysis similar to “1) Treatment period Hb at each evaluation time point in the treatment period” should be conducted by the type of previous ESA formulation (epoetin alfa or epoetin beta, darbepoetin alfa, epoetin beta pegol). Conversion, Conversion (Hb value ≥ 11.0 g/dL), and Conversion (Hb value < 11.0 g/dL) cohorts should be analyzed, and the data should be summarized in the MT-6548 group only. The time course diagram of the means should be prepared separately by treatment group.

4) Analysis by dose of previous ESA formulation types

An analysis similar to “1) Treatment period Hb at each evaluation time point in the treatment period” should be conducted for weekly dose (darbepoetin alfa, epoetin beta pegol: ≥ 15 µg and < 15 µg, 2 classifications) of previous ESA formulation by type (epoetin alfa or epoetin beta, darbepoetin alfa, epoetin beta pegol). The number of patients classified by dose was set to be almost equal.

Conversion, Conversion (Hb value ≥ 11.0 g/dL), and Conversion (Hb value < 11.0 g/dL) cohorts should be analyzed, and the data should be summarized in the MT-6548 group only. The time course diagram of the means should be prepared separately by treatment group.

5) Analysis of Hb value on the first day of the treatment period

An analysis similar to “1) Treatment period Hb at each evaluation time point in the treatment period” should be conducted for the Hb value on the first day of the treatment period (divided the number of subjects into 3 categories at tertiles). The Conversion (Hb value < 11.0 g/dL) cohort should be summarized in the MT-6548 group only. Time course diagram for mean and 95% CI should be prepared separately by treatment group. No statistical test will be conducted for group differences and the difference between baseline and each evaluation time point in the treatment period for the darbepoetin alfa group in the Conversion cohort and Conversion (Hb value ≥ 11.0 g/dL) cohort.

6) MT-6548 group only: analysis with or without iron supplements and iron-containing phosphate binders

An analysis similar to “1) Treatment period Hb at each evaluation time point in the treatment period” should be conducted for subjects continuously using iron supplements or iron-containing phosphate binders and subjects never using iron supplements and iron-containing phosphate binders during the treatment period. No analysis using the MMRM model will be conducted for patient cohorts.

7) MT-6548 group only: analysis by iron supplements and iron-containing phosphate binders formulations

Confidential

An analysis similar to “1) Treatment period Hb at each evaluation time point in the treatment period” should be conducted for subjects using iron supplements or iron-containing phosphate binders continuously during the treatment period, except for the analysis using the MMRM model. No analysis will be performed for patient cohorts.

8) Analysis of Hb value at Week 24 and CRP values on the first day of the treatment period

For MT-6548 group only, a scatter plot chart should be provided after linear regression with the following variables.

No analysis will be performed for patient cohorts.

x: Logarithmic CRP value on the first day of the treatment period

y: Hb value at Week 24 of the treatment period

(2) Proportion of subjects with mean Hb values within the target range (≥ 11.0 to < 13.0 g/dL), < 11.0 g/dL, and ≥ 13.0 g/dL at each evaluation time point in the treatment period

The number, proportion, and 95% CI (Clopper-Pearson [Exact] method) for the proportion of subjects with Hb values within the target range (11.0 g/dL to < 13.0 g/dL, within), < 11.0 g/dL (below), and ≥ 13.0 g/dL (above) at each time point of the treatment period should be provided by treatment group. McNemar tests should be used for before and after comparison (ratio of subjects within the target range and out of target range) on the first day and each evaluation time point of the treatment period.

Point estimate, its 95% CI (exact method), and p-value (Fisher's exact test) of subject proportions should be calculated for the between-group difference (MT-6548 – darbepoetin) of Hb values in each category (within the target range [11.0 g/dL to < 13.0 g/dL], < 11.0 g/dL or ≥ 13.0 g/dL) at each evaluation time point of the treatment period.

The proportion of subjects in each Hb category (within the target range [11.0 g/dL to < 13.0 g/dL], < 11.0 g/dL or ≥ 13.0 g/dL) at each evaluation time point of the treatment period should be provided as a stacked bar graph assuming that the number subjects of each treatment group at the evaluation time point is 100%. Stacked bar charts should be generated separately for each treatment group. The Conversion (Hb value < 11.0 g/dL) cohort should be analyzed only in the MT-6548 cohort. No statistical test will be conducted for the group difference and the difference between baseline and each evaluation time point in the treatment period for the darbepoetin alfa group in the Conversion cohort and Conversion (Hb value ≥ 11.0 g/dL) cohort.

(3) Number of days from the first day of the treatment period required to reach the target Hb range (≥ 11.0 g/dL to < 13.0 g/dL)

Descriptive statistics should be calculated for number of days required from the first day to reach target Hb range (11.0 g/dL to < 13.0 g/dL) of the treatment period. The number of days should be calculated as the first evaluation date reached target Hb range (11.0 g/dL to < 13.0 g/dL) – first date of the treatment period + 1. If target Hb range (11.0 g/dL to < 13.0 g/dL) is not reached, the final date of evaluations – first date of the treatment period + 1 should be assumed.

Confidential

Kaplan-Meier plots for the number of days required from the first day to reach target Hb range (11.0 g/dL to <13.0 g/dL) of the treatment period should be provided by treatment group.

No subjects with an Hb value of ≥ 11.0 g/dL on the first day of the treatment period will be included in the calculation.

Only the Correction and Conversion (Hb value < 11.0 g/dL) cohorts will be analyzed. The Conversion (Hb value < 11.0 g/dL) cohort will be tabulated in the MT-6548 group only.

(4) Hb increase rate

Descriptive statistics should be calculated for the Hb increase rate (g/dL/week) by treatment group. Between-group comparisons by analysis of covariance (ANCOVA) should be performed using Hb on the first day of the treatment period as a covariate. LSMean, its standard errors, and 2-sided 95% CI of Hb increase rate (g/dL/week) should be calculated by treatment group. The point estimate of the between-group difference (MT-6548 – darbepoetin) of LSMean, its standard errors, 2-sided 95% CI, and p-value should be calculated.

The Hb increase rate should be analyzed by 2 methods defined in the “4.10 Hb increase rate”.

Only the Correction and Conversion (Hb value < 11.0 g/dL) cohorts will be analyzed. The Conversion (Hb value < 11.0 g/dL) cohort will be tabulated in the MT-6548 group only.

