5.3 Randomization methods

5.3.1 Randomization and allocation methods

Personnel responsible for preparation of the allocation table will prepare a randomized key code table using block allocation according to stratification factors in accordance with the standard operating procedure for randomized key code table preparation and storage. Subjects deemed eligible to transition to the treatment period will be assigned to treatment groups, lower randomized number first, in accordance with the randomized key code table for each stratification factor. The online enrollment system will then issue a notification of treatment group allocation. The investigator/subinvestigator will prescribe to each subject the correct study drug for his or her treatment group. Further details regarding randomization methods are enumerated in the standard operating procedure for randomized key code table preparation and storage.

Randomized allocation will be performed according to the stratification factors described below such

that the MT-6548 group and the darbepoetin groups are the same size.

- ✓ Correction cohort or conversion cohort
- ✓ Mean Hb during screening period (mean of latest two measurements from central testing facility):
 - Correction cohort: <10.0 g/dL or ≥ 10.0 g/dL
 - Conversion cohort: <11.0 g/dL or ≥ 11.0 g/dL

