8.5.2 Analysis of other endpoints

(1) Changes in mean Hb values from the first day of the treatment period at Weeks 48 and 52 of the treatment period

Descriptive statistics for change from Hb on the first day of the treatment period to mean Hb at Week 48 and Week 52 in the treatment period should be calculated by treatment group. A paired t-test should be performed for before and after comparison of changes from the first day of the treatment period.

A group comparison should be conducted for the change from the first day of the treatment period using the MMRM (with compound symmetry [CS] for a covariance matrix within subject variance). LSMean, its standard errors, and 2-sided 95% CI for change from Hb on the first day of the treatment period to mean Hb at Week 48 and Week 52 in the treatment period should be calculated by treatment group. The point estimate, its standard errors, 2-sided 95% CI, and p-value of the between-group difference (MT-6548 – darbepoetin) of LSMean should be calculated.

Only the Correction and Conversion (Hb < 11.0 g/dL) cohorts should be analyzed. The Conversion (Hb < 11.0 g/dL) cohort should be summarized in the MT-6548 group only.

(2) Proportion of subjects with a ≥ 1.0 g/dL increase in mean Hb values from the first day of the treatment period at each time point of the treatment period.

The number and proportion of subjects and 95% CI (Clopper-Pearson [exact] method) of the proportion of subjects with an Hb value increase of ≥ 1.0 g/dL from the first day to each evaluation time point of the treatment period should be provided.

The estimate, its 95% CI (exact method), and p-value (Fisher's exact test) for between-group difference (MT-6548 – darbepoetin) should be calculated for the proportion of subjects whose Hb level increased by ≥ 1.0 g/dL at each evaluation time point from the first day of the treatment period.

Only the Correction and Conversion (Hb < 11.0 g/dL) cohorts should be analyzed. The Conversion (Hb < 11.0 g/dL) cohort should be summarized in the MT-6548 group only.

(3) Number of days to maintain the target Hb values

The number of maintenance days should be calculated from reaching to leaving the target Hb range for each subject, and the descriptive statistics should be calculated. Only the MT-6548 group is analyzed. However, if treatment period is completed in 52 weeks, the maintenance days should be until Week 52 of the treatment period. No analysis will be performed for patient cohorts.

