2.3 Randomization methods

Personnel responsible for preparation of the allocation table should prepare a randomized key code table using block allocation according to stratification factors in accordance with the standard operating procedure for randomized key code table preparation and storage. Subjects who are judged eligible to enter the treatment period are assigned to treatment groups in ascending order of the randomization number based on the randomization key code table for each stratification factor, and the treatment groups assigned on the Web registration system are notified. The investigator/coinvestigator should prescribe the study drug of the treatment group notified on the

Web registration system. Further details of randomization methods shall be specified in the standard operating procedure for randomization key code table preparation and storage.

Subjects should be randomly assigned in a 1:1 ratio to MT-6548 and darbepoetin groups with the following stratification factors.

- ✓ Correction cohort or Conversion cohort
- ✓ Mean Hb values during the screening period (mean of the latest two central measurements):
- Correction cohort: $<10.0 \text{ g/dL}$ or $\geq 10.0 \text{ g/dL}$
- Conversion cohort: $<11.0 \text{ g/dL}$ or $\geq 11.0 \text{ g/dL}$

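### The Phase 1 SAP reports the randomised Conversion (Hb <11.0) stratum without its darbepoetin arm for all four secondary endpoints, and the two SAPs disagree on this rule

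*SAP*

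**What the plan says.** Allocation is stratified. Protocol 5.3.1 states that "Randomized allocation will be performed according to the stratification factors described below", and for this cohort the levels are "Conversion cohort: <11.0 g/dL or ≥ 11.0 g/dL". SAP 2.3 confirms the ratio: "Subjects should be randomly assigned in a 1:1 ratio to MT-6548 and darbepoetin groups with the following stratification factors". The sample-size rationale (Protocol 6.1; SAP 2.5 in both plans) says cohort sizes were chosen so that each cohort, including Conversion subjects with Hb <11.0, could be evaluated.

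Section 8.5 of each SAP sets a default: efficacy analyses are repeated by patient cohort unless stated otherwise. The Phase 1 SAP then departs from it for Conversion (Hb <11.0):

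- Hb at each time point and target-range proportions, 8.5.2 (1) and (2): "should be analyzed only in the MT-6548 cohort".
- Days to target and Hb increase rate, 8.5.2 (3) and (4): "cohort will be tabulated in the MT-6548 group only".
- Baseline-Hb tertiles, 8.5.2 (1) 5), and change in mean Hb and ≥1.0 g/dL responders, 8.5.3 (1) and (2): MT-6548 group only.

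The final SAP repeats the rule for change in mean Hb in its 8.5.2 (1): "cohort should be summarized in the MT-6548 group only". It also keeps it for responders, the tertiles and days to target. Neither SAP gives a reason, and each declares no change from the protocol.

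**The concern.** Subjects enter this stratum because their mean screening Hb was below 11.0 g/dL, and the target range starts at 11.0. Regression to the mean alone will move some of them upward and into range. The dosing algorithms of both arms (Protocol 8.3.1 and 8.3.2) also step the dose up when Hb is below 11.0, so titration pushes Hb the same way.

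The planned MT-6548 paired t-tests and McNemar tests compare later visits with the first treatment day, and cannot separate these influences from drug effect. The darbepoetin subjects in the stratum share the selection and visit schedule and are also titrated upward from below 11.0, so they are the natural reference. The primary MMRM is not run by cohort, so it supplies no controlled estimate for this stratum either.

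**Working it through.** **1. The plan's own figure.** Inputs from SAP 2.5: 150 per arm, SD 1.78, margin −0.75, true difference 0, two-sided 5%.

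SE = 1.78 × √(2/150) = 0.2055. Power = Φ(0.75/0.2055 − 1.96) = Φ(1.69) = 95.4%. A noncentral-t calculation, and a simulation that also required the MT-6548 CI to lie within 11.0–13.0, both give 95.3%. The stated figure of more than 95% reproduces and is not in question.

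**2. Where the control is dropped in Conversion (Hb <11.0).**

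| Output | Protocol (5.4.1, 13.3.2) | Phase 1 SAP | Final SAP |
|---|---|---|---|
| Hb at each time point | No arm restriction | MT-6548 only | No such rule; the default gives both arms |
| Target-range proportions | No arm restriction | MT-6548 only | No such rule; the default gives both arms |
| Days to target | Correction only | MT-6548 only | MT-6548 only |
| Hb increase rate | Correction only | MT-6548 only | Not an endpoint |
| Change in mean Hb | Correction only | MT-6548 only | MT-6548 only |
| ≥1.0 g/dL responders | Correction only | MT-6548 only | MT-6548 only |
| Hb by baseline-Hb tertile | Not specified | MT-6548 only | MT-6548 only |

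The rule also appears for haematocrit, red cell count and reticulocytes (Phase 1 SAP 8.5.3 (11); final SAP 8.5.2 (11)), and for the additional tabulation of Hb increase rate >0.5 g/dL/week in Phase 1 SAP 8.6.10.

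**3. Internal conflict on responders.** Phase 1 SAP 8.5.3 (2) limits responders in this cohort to MT-6548. The Week 24 responder analysis in 8.5.4.6 uses the same ≥1.0 g/dL definition, names the same cohort and asks for a between-group difference with CI and p-value. The final SAP repeats the conflict at Week 52: 8.5.2 (2) against 8.5.4.5 (3).

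**4. Size of the stratum.** The Conversion target is 200, with at most 120 in each Hb stratum. The <11.0 stratum then holds 200 − 120 = 80 up to 120 subjects, or 40 to 60 per arm at 1:1, before dropout.

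**5. Precision if both arms are shown.** Half-width = t(0.975, 2n−2) × 1.78 × √(2/n):

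- n = 40: 1.991 × 1.78 × 0.2236 = 0.79 g/dL
- n = 60: 1.980 × 1.78 × 0.1826 = 0.64 g/dL

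The normal quantile 1.96 gives 0.78 and 0.64. SD 1.78 is the upper 80% confidence limit from Week 6 of another study, so it is probably high. With an SD of 1.0, which is my assumption and not in the documents, the normal-quantile half-width would be 0.44 to 0.36.

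**6. What it cannot support.** Power against −0.75 within the stratum, Φ(0.75/(1.78√(2/n)) − 1.96), is 47% at 40 per arm and 64% at 60.

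**The case against.** The strongest case against is that the gap is narrower than it looks, and much of that case stands.

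- A reader might infer that both SAPs drop the control throughout. They do not. The final SAP has no such rule for Hb by visit or target-range proportions. Its treatment period runs from the first day to Week 52, so a controlled Hb course for this stratum, including the early visits, appears to be planned there.
- A reader might infer that planned protocol comparisons were removed across the board. For days to target, increase rate, change and responders, the protocol asks for the Correction cohort only. There the SAP adds an uncontrolled Conversion analysis. Only for Hb by visit and target-range proportions does it narrow what the protocol left open to both arms.
- A reader might infer that the stratum has no controlled output at all. The responder subgroup analyses, Hb ≥13.0/≥14.0 and <9.0/<8.0 by cohort, and adverse events by cohort are all given by treatment group.
- For the whole Conversion cohort and Conversion (Hb ≥11.0), the rules withdraw tests, not darbepoetin data. No defect is shown there.
- The sizing text promises evaluation, not a between-arm comparison, and secondary and other endpoints are declared exploratory (Phase 1 SAP 8.5.4.7).

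These points limit scope and weight. They do not explain why one randomised stratum alone loses its comparator in the Phase 1 tables, why the two SAPs differ on the same endpoints, or why each SAP gives two instructions for the same responder definition.

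**Conclusion.** The concern holds in limited form. In the Phase 1 SAP, the Conversion (Hb <11.0) stratum is analysed in MT-6548 only for all four secondary endpoints, the tertile analysis, and change and responders, with no reason given. The final SAP keeps the rule for the tertiles, days to target, change and responders. The plans therefore disagree with each other on Hb by visit and target-range proportions, and each disagrees with itself on responders.

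The effect is on interpretation of exploratory results. The primary non-inferiority analysis is untouched. A controlled comparison would be useful as an estimate, with a half-width of about 0.64 to 0.79 g/dL. That rests on SD 1.78, 200 Conversion subjects enrolled, 1:1 allocation and no dropout; dropout would widen it and a smaller SD would narrow it. It would be tempting to read the stratum as supporting its own non-inferiority conclusion, but 47% to 64% power does not allow that. The change should be made, but nothing confirmatory depends on it.

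**What to change.** Delete the MT-6548-only rule specific to Conversion (Hb <11.0) wherever it appears in either SAP. Show darbepoetin alongside, with the between-group difference and 95% CI as for the Correction cohort. State that the comparison is exploratory and carries no separate non-inferiority claim. This brings Hb by visit and target-range proportions into line across the two SAPs and resolves the responder conflict in each.

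If the sponsor prefers to keep the restriction, it should give the reason and list it under changes from the protocol.

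No new data are needed. The cost is extra table columns and comparison code already required for Correction. The final SAP (8.5.4.3) records that the Phase 1 analysis has been conducted, so comparisons added after that lock should be labelled as added analyses, with the reason, under Protocol 13.4.

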12.1 Withdrawal criteria

Subjects will be withdrawn from the study if the following criteria are met:

- (1) If the subject expresses a desire to withdraw from the study.
- (2) If it is discovered that the subject is clearly ineligible for study participation.
- (3) If investigators/subinvestigators determine that AEs make continued participation in the study difficult.
- (4) If the subject meets one of the following criteria regarding hepatic function abnormalities during the study.
 - 1) ALT or AST > 3x ULN and total bilirubin > 2x ULN
 - 2) ALT or AST > 3x ULN and INR > 1.5^{*1}
 - 3) ALT or AST > 8x ULN
 - 4) ALT or AST remains > 5x ULN over 2 weeks^{*2}
 - 5) ALT or AST > 3x ULN with symptoms including e.g., fatigue, nausea, vomiting, right upper quadrant pain, fever, rash or eosinophilia

*1: The subject should be withdrawn from the study if the measurement of PT-INR is performed besides this study and the value meets the criterion.

*2: Administration of the study drug should be avoided with ALT or AST > 5x ULN unless there are no other good therapeutic options.

- (5) If rescue therapy is performed prior to conclusion of scheduled tests at Week 24.
- (6) If investigators/subinvestigators determine that continuation of the study is inappropriate for a subject, such as if hyperviscosity syndrome occurs or if control of Hb within the target range is impossible.
- (7) If continuous haemodialysis or peritoneal dialysis is initiated, or if the subject receives a renal transplant.
- (8) If pregnancy of the subject is discovered.
- (9) If the investigator/subinvestigator determines a subject should withdraw from the study for any other reason.

Rationale

- (1) Set out of ethical considerations.
- (2) (7) Set in order to prevent study drug administration to subjects unsuitable for inclusion in safety

or efficacy evaluation.

- (3) (4) (6) (8) Set out of safety considerations.
- (5) Set because evaluating efficacy of MT-6548 accurately would be difficult.
- (9) Set in order to allow the investigator/subinvestigator to make determinations regarding study continuation for significant safety-related reasons other than those enumerated above.

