2.5 Rationale for sample size

A total of 300 subjects (150 each for the MT-6548 and darbepoetin groups) should be enrolled in the treatment period. The target sample size for each cohort is shown below.

- ✓ Correction cohort: 100 subjects
- ✓ Conversion cohort: 200 subjects

However, the maximum number of subjects with mean screening period Hb values (mean of 2 most recent central testing facility results) of <11.0 g/dL and ≥ 11.0 g/dL in the screening period in the Conversion cohort should be 120.

[Rationale]

For the primary efficacy endpoint of mean Hb values at treatment period Weeks 20 and 24, the mean Hb value in the darbepoetin group is assumed to be 12.0 g/dL, the difference between the MT-6548 and darbepoetin groups is assumed to be 0 g/dL, and the standard deviation for both is assumed to be 1.78 g/dL. The non-inferiority margin is set at -0.75 g/dL. Calculation of statistical power from these assumptions shows that a sample size of 150 subjects in each group would ensure greater than 95% probability that the mean of mean Hb values in the MT-6548 group and their 95% CI would fall within the target Hb range (≥ 11.0 to < 13.0 g/dL) and non-inferiority could be established.

In addition, the target sample size was set for each of the Correction cohort, Conversion cohort, Conversion (Hb value ≥ 11.0 g/dL) cohort, and Conversion (Hb value < 11.0) cohort so that appropriate evaluation could be made for each cohort.

The assumed standard deviation was set at 1.78 g/dL based on the upper limit of the 80% confidence interval of the standard deviation in the MT-6548 300 mg group at Week 6 in study CI-0021.

3. Endpoints

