8.1 Basic Matters

8.1.1 Level of significance and confidence coefficient

When implementing tests, level of significance should be set at 2-sided 5%. Confidence interval will be 2-sided with a confidence coefficient of 95%.

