8.5 Efficacy analysis

As a general rule, efficacy analysis will be performed on the FAS. When necessary, descriptive statistics for continuous variables should be calculated and frequency and proportion will be calculated for discrete variables. Unless otherwise specified, a similar analysis will be conducted for patient cohort. No data from the day after the rescue therapy implementation date should be included in the efficacy analysis.

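### Per-visit target-range and ≥1.0 g/dL responder rates are in effect observed-case, so subjects rescued or withdrawn for uncontrolled Hb drop out instead of counting as failures

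*SAP*

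**What the plan says.** **Endpoints.** Phase 1 SAP 8.5.2(2) and Final SAP 8.5.1(3) classify Hb at each visit as within, below or above target, with exact intervals and Fisher p-values for the difference between arms. No group test is done in the Conversion or Conversion (Hb ≥11.0) cohorts. Phase 1 SAP 8.5.3(2) and Final SAP 8.5.2(2) do the same for a rise of at least 1.0 g/dL: the between-arm estimate, interval and p-value "should be calculated for the proportion of subjects whose Hb level increased" by that amount. Because Conversion (Hb <11.0) is summarised for MT-6548 only, this comparison exists only in the Correction cohort.

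**Denominator.** It is written once, for the stacked bar chart of Hb categories: "assuming that the number subjects of each treatment group at the evaluation time point is 100" per cent. The dose-distribution chart in Phase 1 SAP 8.5.3(5) uses the whole treatment group instead. The tables and tests name none. Section 8.5 of each SAP puts efficacy on the FAS as a general rule.

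**How subjects leave.** Protocol 12.1(5) withdraws anyone rescued before the Week 24 tests are finished. Protocol 12.1(6) lets the investigator withdraw a subject, "such as if hyperviscosity syndrome occurs or if control of Hb within the target range is impossible". Under Protocol 8.5.3 rescue means ESA, transfusion or phlebotomy, and a subject rescued after Week 24 may stay. Section 8.5 of each SAP adds: "No data from the day after the rescue therapy implementation date should be included in the efficacy analysis". Sections 7.1 and 7.2 leave missing values missing and do not fill from outside the visit window. Section 7.4 also outputs LOCF values at Week 24 or Week 52 for laboratory efficacy endpoints. Neither SAP says how a rescued or withdrawn subject is classed in these proportions.

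**The concern.** Withdrawal and rescue depend on the variable being classified. A subject whose Hb falls far enough to need ESA, or cannot be kept in range, is the clearest failure on a target-range endpoint. Under these rules that subject becomes neither below nor above target at later visits and is simply absent. The arm that loses more such subjects looks better among those who remain.

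Unequal loss is plausible. The trial is open-label and 12.1(6) is a judgement. Under Protocol 8.5.3 extra darbepoetin is never rescue for a control subject, even outside the adjustment algorithm. ESA in the MT-6548 arm is prohibited except as rescue, and before Week 24 rescue means withdrawal. The same handling carries into the responder and target-achievement subgroup tables (Phase 1 SAP 8.5.4.6; Final SAP 8.5.4.5).

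**Working it through.** **The plan's own figure.** The only design calculation concerns the primary endpoint. Inputs (SAP 2.5 and 8.1.1): "The non-inferiority margin is set at -0.75 g/dL"; "the difference between the MT-6548 and darbepoetin groups is assumed to be 0 g/dL"; "the standard deviation for both is assumed to be 1.78 g/dL"; "level of significance should be set at 2-sided 5" per cent; 150 per arm.

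- Standard error = 1.78 × √(2/150) = 0.2055.
- Power ≈ Φ(0.75/0.2055 − 1.96) = Φ(1.69) = 0.954.
- A simulation of the joint criterion (non-inferiority, and the MT-6548 interval inside 11.0 to 13.0) gives 0.953.

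The stated figure of more than 95% is reproduced. It does not depend on the responder tables.

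**Is the rate observed-case?** Within, below and above cover every possible Hb value, and there is no category for no data. The chart is explicitly scaled to subjects at the visit. A table with an FAS denominator would have proportions summing to less than 100% and would disagree with its own chart. With missing values left missing and post-rescue Hb dropped, at-visit is the natural reading. It is an inference, not a stated rule.

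**Size of the effect.** Let p be the rate among subjects with an Hb at the visit and d the proportion lost to rescue or Hb-related withdrawal. With everyone else observed and the lost counted as failures:

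- all-FAS rate = p × (1 − d), so the observed rate is too high by the factor 1/(1 − d): 1.05, 1.11, 1.18 and 1.25 for d = 5, 10, 15 and 20%;
- with equal p in both arms, the all-FAS difference is −p × (d for MT-6548 − d for darbepoetin).

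The documents give neither p nor d, so both are assumptions. At p = 70% with d = 15% versus 5%, 0.70 × 0.85 = 59.5% and 0.70 × 0.95 = 66.5%, a difference of −7.0 points where the observed-case table shows 0. At 10% versus 5% it is −3.5 points. At 15% in both arms the difference stays 0, but each rate is 59.5%, not 70%.

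The table uses whole subjects, with 150 per arm, or 50 per arm for the Correction cohort (100 planned, allocated 1:1). The 42.6% row takes p from the plan's own mean of 12.0 and SD of 1.78 under normality: 2Φ(1/1.78) − 1 = 0.426.

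| Per arm | p | Lost, MT-6548 vs darbepoetin | Observed-case | All-FAS | All-FAS difference (Fisher p) |
|---|---|---|---|---|---|
| 150 | 42.6% | 15% vs 5% | 54/128 = 42.2% vs 60/142 = 42.3% | 36.0% vs 40.0% | −4.0 points (0.55) |
| 150 | 60% | 10% vs 10% | 81/135 = 60.0% in both | 54.0% in both | 0 (1.00) |
| 150 | 60% | 15% vs 5% | 77/128 = 60.2% vs 85/142 = 59.9% | 51.3% vs 56.7% | −5.3 points (0.42) |
| 150 | 70% | 20% vs 5% | 84/120 = 70.0% vs 99/142 = 69.7% | 56.0% vs 66.0% | −10.0 points (0.10) |
| 50 | 70% | 20% vs 5% | 28/40 = 70.0% vs 34/48 = 70.8% | 56.0% vs 68.0% | −12.0 points (0.30) |

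The observed-case differences in these rows are all within 1 point of zero.

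**The case against.** A reader might infer that the SAP prescribes an at-visit denominator for the tests. It does not: the quoted sentence governs the chart only, and an FAS denominator is not excluded. The lists of output tables, which might settle it, are not in the copy reviewed. This limits the point to an unstated denominator whose natural reading is observed-case.

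A reader might also infer that LOCF turns failures into successes. The documents do not support that as a general statement. The standard ESA rescue route requires at least two weeks at maximum dose, aggravated anaemia and Hb below 8.0, and Hb on the day of rescue is still usable, so the carried value will often be out of range already. An in-range value before rescue belongs mainly to the acute or discretionary route. What stands is that LOCF classes the subject by the last usable value, not by the rescue, and the SAP does not say that LOCF applies to these proportions.

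The failures are reported elsewhere: rescue by arm and interval with Fisher tests, discontinuations by reason, and Hb extremes in the safety set. A marked imbalance would be seen. But these separate tables do not give a per-visit rate with failures counted.

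A blanket non-responder rule would also mislabel subjects. Phlebotomy and hyperviscosity reflect too much response, not a failure to rise by 1.0 g/dL. That is correct and shapes the fix. More broadly, composite versus observed-case is an estimand choice. This is a reason to show both.

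**Conclusion.** The concern holds in a limited form. As written, the plan lets subjects who fail on Hb leave the per-visit target-range and ≥1.0 g/dL rates, and nothing classes them as failures. The overstatement is a factor of 1.05 to 1.25 if 5 to 20% are lost. In the unequal-loss examples the all-FAS difference is about 4 to 10 points with 150 per arm and 12 points in the Correction cohort, against almost none observed. These sizes rest entirely on assumed rates and on all the losses being Hb failures. With equal loss the difference is not biased, though both rates are too high. The documents do not show which arm would lose more.

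It would be wrong to read this as a threat to the non-inferiority conclusion. That rests on a separate MMRM with tipping-point and LOCF-ANCOVA sensitivity analyses, and Phase 1 SAP 8.5.4.7 treats secondary and other endpoints as exploratory without multiplicity adjustment. None of the all-FAS differences shown reaches the 5% level. This is a cheap improvement to descriptive results that readers are likely to quote.

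**What to change.** 1. State the denominator for each proportion, in tables, tests and charts alike.
2. Add a version of each proportion and its between-arm comparison on all FAS subjects in the relevant cohort, including the subgroup responder and achievement rates.
3. For target range, count a subject as not in range at visits after any rescue or after withdrawal under Protocol 12.1(5) or (6).
4. For the ≥1.0 g/dL rise, count as non-responders only subjects with ESA or transfusion rescue or withdrawal for low Hb. Show phlebotomy, hyperviscosity and high-Hb withdrawals separately.
5. Show other missing values as a no-data category, and keep the observed-case tables alongside.

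Rescue details and the dates and reasons for withdrawal already go into the CRF, so no new data are needed. The SAP should state how low-Hb and high-Hb withdrawals are told apart if the recorded reason does not say. The cost is SAP wording, a few more tables and somewhat less favourable rates. Nothing in clinical management changes.
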